4.1 Phase 1: Evidence synthesis

Our evidence synthesis will comprise three components: (1) an IPD meta-analysis of prospective studies considering individuals meeting ARMS criteria to identify factors that show consistent evidence of prognostic value; (2) a narrative systematic review and quality appraisal of existing prognostic models to inform subsequent model updating and aggregation activities at Phase 2; and (3) a focused review for economic evaluations of health care for people at risk of psychosis and for first episode of psychosis, to inform the health economic model evaluated at Phase 3.

Our synthesis will follow state-of-the-art guidelines for IPD meta-analytic syntheses in prognostic research [26, 27], and our outputs will comply as a minimum with the PRISMA statement for the reporting of IPD meta- analysis [28] and the Transparent Reporting of a Multivariable Prediction Model for Individual Prognosis or Diagnosis (TRIPOD) reporting guidelines [29, 30]. Our review protocol will be published on the HTA website and on a specific register of systematic review protocols (PROSPERO) to allow for independent scrutiny of all outputs against our planned review and analytic strategy.

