4.1.1 IPD meta-analysis of prognostic factors

Study selection criteria: The following selection criteria will be used:

Population: Individuals meeting ARMS criteria, defined as 1) attenuated psychotic symptoms, 2) full-blown intermittent psychotic symptoms and 3) genetic/familial risk for schizophrenia in conjunction with a significant decrease in functioning and operationalised using suitable measures such as the Comprehensive Assessment of At-Risk Mental States (CAARMS) [31] or the Structured Interview for Prodromal Syndromes (SIPS) [32].

Unlike previous aggregate data meta-analyses of this research area [e.g. 33], we will not consider prospective studies that only assessed for the presence of "basic symptoms" of psychosis i.e. subtle subjective cognitive and perceptual disturbances shown to predict onset of first episode psychosis [34, 35]. Basic symptoms are in fact distinct from the ARMS criteria and are not used in the NHS.

Study design: Any prospective study (i.e. cohort studies as well as randomised controlled trials of preventive interventions) with participants meeting the above-mentioned ARMS criteria will be eligible. Studies must include at least 12-month follow-up longitudinal assessments and collected data on psychosis transition in ARMS individuals.

Outcomes: Our primary outcome will be psychosis transition at 12-month follow-up assessments defined using standard diagnostic classification systems (DSM-III, DSM-IV, DSM-5, ICD-10, ICD-11) or commonly used ARMS assessment schedules (e.g. SIPS or CAARMS). Secondary outcomes will include psychosis transition at subsequent available follow-up assessments (18-month, 24-month etc) and time to transition (time to event).

Identifying studies - information sources: Database searches will be conducted on PsychInfo, PubMed, EMBASE and CINAHL. No restriction will be placed on language of publication but the searches will be restricted to 1994 onwards, the initial year of the first prospective study using ARMS criteria [36, 37]. Database searches will be supplemented by 1) inspection of studies included in previous systematic reviews and meta-analyses of psychosis transition studies; 2) inspection of reference lists of psychosis transition studies identified through the database searches.

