4.1.3 Review of economic evaluations for health economic modelling

In addition to the reviews above, we will run a systematic, focussed search for economic evaluations of health care for people at risk of psychosis and for first episode of psychosis, to inform the economic model considered in subsequent components of the project.

Search strategy: The search strategy used for our IPD meta-analysis will be modified to specifically identify relevant health economics literature. More specifically, titles, abstracts and keywords will be searched in the publication databases using the search filter developed to identify economic evaluations for NHS EED with the clinical terms identified for the reviews above (an example search strategy for EMBASE is shown in Appendix 1) [50]. The databases searched will include EMBASE, CINAHL, EconLit, All EBM Review, Medline and PsychInfo.

Study selection criteria

Population: We will use the same population criteria as the IPD meta-analysis.

Study design: Full and partial economic evaluations (including cost of illness/economic burden of disease studies) published in the previous 20 years at the time of the search will be included. These can be prospective, retrospective and economic model study designs as well as systematic reviews of economic evidence. Studies must include formal cost and/or health benefit measures and analyses. Editorials and other descriptive studies (e.g. historical discussion and case reports) will be excluded.

Intervention and comparators: No specific interventions or comparators will be specified since the review will be used to identify data about the costs and health benefits of care following transition to psychosis.

Outcomes: Studies must include one or more of the following measures: health and social care service use, direct or indirect costs, preference based utility or health status measures or quality adjusted life years (QALYs).

Only studies published in English will be included.

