It is anticipated that a Markov cohort model [89] will be an appropriate vehicle to capture transition between at risk, treated health states and the longer term recovery/relapse cycle of psychosis. The model will synthesise data from several sources to estimate the probability, costs and health benefits of events/health states. These include the data collected in Phases 1-3 to estimate probability of transition between risk states, with and without the prognostic tool, the costs and health benefits of the different risk states with and without appropriate treatment, the costs and health benefits of recovery and relapse states for psychosis. Data from systematic reviews, meta-analysis and controlled trials will be preferred to data from other sources. Probabilistic sensitivity

analysis will be used to account for data uncertainty in all analyses. Structural uncertainty will be assessed in the sensitivity analyses, threshold and scenario analyses outlined above.

5. Research timetable

The overall project will be undertaken over 51 months (01/10/18 - 31/12/22).

Phase 1 (evidence synthesis) will be completed within 16 months (01/10/18 – 01/02/2020). Prior to the start of the project, we will continue to consolidate our collaborative network and invite principal investigators of relevant ARMS cohort studies to join this collaboration. Between 01/10/18 to 01/01/19 we will finalise our review protocols and literature searches to identify all relevant IPD sets. The retrieval and processing of IPD will be completed by 31/11/19. In parallel, we will conduct the systematic review of multivariable prognostic models in the ARMS group (completed by 31/12/2019) and the focused health economic review. Data-analysis will be completed in parallel with the Phase 2 analyses (01/12/19 – 31/03/20). The Phase 1 findings will be written-up for publication by the 31/06/2020. In terms of health economic analyses, development and validation of decision analytic model structure and assumptions will be completed by 31/03/20. Estimation and validation of probability, cost and health benefit variables, initial analyses and model verification will take place between 01/04/20 and 31/10/22.

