Appendix 1 - EXAMPLE SEARCH FOR THE ECONOMIC EVAULUATIONS REVIEW (EMBASE)

- 1 psychosis/ or psychosis.mp.
- 2 (clinically at high risk or clinically at risk or clinical high risk or ultra-high risk or prodrom* or at risk mental state or risk of psychosis or ARMS or prodromal psychosis).mp.
- 3 1 and 2
- 4. Health Economics/
- 5. exp Economic Evaluation/
- 6. exp Health Care Cost/
- 7. exp Pharmacoeconomics/
- 8. 6 or 7 or 8 or 9
- 9. (econom\$ or cost or costs or costly or costing or price or prices or pricing or pharmacoeconomic\$).ti,ab.
- 10. (expenditure\$ not energy).ti,ab.
- 11. (value adj2 money).ti,ab.
- 12. budget\$.ti,ab.
- 13. 11 or 12 or 13 or 14
- 14. 10 or 15
- 15. letter.pt.
- 16. editorial.pt.
- 17. note.pt.
- 18. 17 or 18 or 19
- 19. 16 not 20
- 20. (metabolic adj cost).ti,ab.
- 21. ((energy or oxygen) adj cost).ti,ab.
- 22. ((energy or oxygen) adj expenditure).ti,ab.
- 23. 22 or 23 or 24
- 24. 21 not 25
- 25. exp Animal/
- 26. exp Animal/
- 27. exp Animal Experiment/
- 28. Nonhuman/
- 29. (rat or rats or mouse or mice or hamster or hamsters or animal or animals or dog or dogs or cat or cats or bovine or sheep).ti,ab.
- 30. 27 or 28 or 29 or 30 or 31
- 31. exp Human/
- 32. exp Human Experiment/
- 33. 33 or 34
- 34. 32 not (32 and 35)
- 35. 26 not 36
- **36.** 3 and 37

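### The economic review is meant to cover first-episode psychosis and care after transition, but its population rule and search terms are those for at-risk people only

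*Protocol*

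**What the plan says.** Protocol section 4.1 lists, as the third component of Phase 1, "a focused review for economic evaluations of health care for people at risk of psychosis and for first episode of psychosis". Section 4.1.3 repeats that scope. Under interventions and comparators it gives the reason for leaving them open: "the review will be used to identify data about the costs and health benefits of care following transition to psychosis".

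The selection criteria in 4.1.3 then state: "Population: We will use the same population criteria as the IPD meta-analysis". The population in section 4.1.1 is "Individuals meeting ARMS criteria, defined as 1) attenuated psychotic symptoms, 2) full-blown intermittent psychotic symptoms and 3) genetic/familial risk for schizophrenia" with a functional decline, measured with the CAARMS, the SIPS or a similar instrument.

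On searching, 4.1.3 combines a published economic-evaluation filter with the clinical terms already used for the other reviews, across six databases. Appendix 1 gives the EMBASE version as an example. Its line 2 begins "clinically at high risk or clinically at risk or clinical high risk or ultra-high risk or prodrom* or at risk mental state" and continues with further at-risk and prodromal terms.

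Section 4.3.12 lists the inputs the decision model needs, among them "the costs and health benefits of recovery and relapse states for psychosis".

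**The concern.** The scope and purpose of the review point to people who already have psychosis. The rules that decide which papers are found and kept point to people who do not yet have it. Two reviewers applying the selection criteria faithfully would reject a cost or utility study in a first-episode cohort, although the section opens by saying such studies are wanted.

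What is at stake is the evidence for the later part of the decision model. The model is to run over 1, 2 and 5 years and to represent recovery and relapse after psychosis onset. This is the only literature review of economic evidence that the protocol plans, and section 4.3.12 prefers data from systematic reviews, meta-analysis and controlled trials. Evaluations that begin at the first episode are an obvious place to look for such inputs.

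**Working it through.** No figure in the protocol is involved, so the check is to set the texts side by side and trace the search logic.

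**Scope against eligibility**

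| Element | Where | At-risk people | First-episode cohorts |
|---|---|---|---|
| Stated scope | 4.1 and opening of 4.1.3 | in | in |
| Stated use | 4.1.3, interventions and comparators | – | post-transition care wanted |
| Population rule | 4.1.3, importing 4.1.1 | in | out |
| Clinical search terms | 4.1.3 search strategy | in | no term |
| Example search | Appendix 1, lines 1–3 | in | no term |
| Model inputs needed | 4.3.12 | yes | recovery and relapse states |

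The second ARMS group in 4.1.1, intermittent psychotic symptoms, does not bridge the gap. The protocol lists it as a way of being at risk, with transition to psychosis as the later outcome.

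**Search logic.** Let P be a record with the psychosis term (Appendix 1 line 1), R a record with an at-risk term (line 2), and E a record that passes the economics filter after its exclusions.

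- Line 3 = P and R.
- Final line = line 3 and E, so retrieved = P and R and E.
- A first-episode evaluation satisfies P and E. Without a line 2 term it fails R and is not retrieved.
- None of the listed lines contains a term for first-episode or early psychosis, or for schizophrenia.

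**Screening.** Some first-episode papers will satisfy R by chance, for example through the truncated prodrome term or the free-text word ARMS. Section 4.1.3 has full texts judged against the selection criteria above it, so those papers then meet the ARMS-only population rule and are excluded.

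**What remains.** The population rule governs who enters a study, not how long they are followed. Section 4.1.3 admits prospective, retrospective and modelling designs and systematic reviews of economic evidence. A study or model that starts with ARMS individuals and continues past transition is therefore eligible and can carry post-transition costs and utilities. An evaluation that starts from a first-episode cohort is not eligible.

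**The case against.** The strongest reply is that the damage is limited. ARMS-based evaluations that extend past transition stay in. Section 4.3.12 says the model draws on several sources and gives an order of preference, so the review is not its sole supply. The cost-effectiveness analysis is labelled exploratory and has probabilistic, threshold and scenario analyses around it. Nothing here touches the prognostic tool, the primary outcome or the external validation. All of that stands, and it bears on the size of the problem. It does not reconcile the scope with the population rule.

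It could also be said that 4.1.3 promises to modify the search and that Appendix 1 is only an example. The modification described is the added economics filter, and the sentence in 4.1.3 fixes the clinical terms for every database. The example follows that sentence faithfully.

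Two stronger readings are tempting. A reader might infer that the review cannot supply any post-transition data; the eligible ARMS-based studies and models contradict that. A reader might also infer that the consenting subsample, with its stated minimum of 100, becomes the only fallback, and size the loss by the transitions expected in it. The protocol does not make the subsample the only alternative. Such a count would also apply the whole-cohort transition rate to an opt-in group and treat a minimum as the expected size.

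**Conclusion.** The protocol contradicts itself: the stated scope of the economic review includes "economic evaluations of health care for people at risk of psychosis and for first episode of psychosis", while its population rule admits ARMS individuals only and its search has no first-episode term. The population rule does the excluding; the search adds a loss of sensitivity.

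The consequence is that one class of evidence, evaluations starting from first-episode cohorts, is ineligible and mostly unseen. A planned source for the psychosis, recovery and relapse states is weakened, not removed. How much this would shift the cost-effectiveness result cannot be derived from the protocol, because it depends on how many ARMS-based evaluations run past transition and on what the other sources provide.

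The conclusion assumes that reviewers apply the criteria as printed. If they were to follow the opening statement of scope, the harm would be smaller, but the selection would then depart from the written rule. The point deserves correction because the review serves one of the project's four aims and the repair is short.

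**What to change.** Make three matching changes:

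1. In 4.1.3, change the population to: 'ARMS as in the IPD meta-analysis, or first-episode psychosis'.
2. In the 4.1.3 search strategy, state that the economics filter is combined with the at-risk clinical terms OR first-episode and early-psychosis terms, in all databases.
3. Make the same change in Appendix 1 line 2, so that the example agrees with the rule.

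Changing the population line and the example alone would leave the 4.1.3 search sentence contradicting both. If the wider search is not wanted, the alternative is to narrow the stated scope in 4.1 and 4.1.3 to at-risk people and name the source of the post-transition inputs.

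The cost is a few sentences of amendment and more records for the two assigned reviewers to screen and extract. The documents give no basis for estimating how many more.

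As a clerical aside, the line references in Appendix 1 should be checked when it is revised. Apart from the reference to line 3 they appear to sit two too high throughout; the last line, 36, cites a line 37. This may come from the PDF conversion, and nothing above depends on it.

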4.2.1 Updating an existing model, to potentially include new prognostic factors

To avoid excess prognostic models with the same aim within the same clinical field we will begin Phase 2 by updating any models identified as statistically valid according to QUIPS [53] and PROBAST [43], and clinically relevant by the focus groups in Phase 1, potentially with additional prognostic factors identified in Phase 1 also.

There are two main approaches for updating clinical prognostic models – regression coefficient updating, and meta-model updating. Regression coefficient updating focuses on updating some or all coefficients from an existing prognostic model, while meta-model updating synchronises multiple existing prognostic models into one new meta-prognostic model [54]. If only small changes exist between the IPD used to develop the model ("original data") and the additional IPD collected as part of Phase 1 ("updating data"), the simple regression coefficient updating method will be sufficient.[54] However, if larger changes are observed more involved methods such as a meta-model approach may be required.[27]

4.2.1.1 Regression Coefficient Updating

There is a hierarchical approach to updating the regression coefficients of an existing model, based on the available information. The most straightforward strategy is to adjust a model's intercept such that the mean predicted probability of the event according to the prognostic model becomes equal to the observed event rate in the updating data (intercept update)[54]. Additional updating methods vary from overall adjustment of the model intercept and the overall calibration slope (logistic calibration), adjustment of a particular regression coefficient, to the re-estimation of included, or the addition of completely new, predictors to the existing model (model revision). The most appropriate

strategy will be determined once we know the results of the Phase 1 evidence synthesis and the initial feedback from the focus groups.

4.2.1.2 Meta-Model Updating

If we identify multiple historical prognostic models for the same or similar endpoints and populations in Phase 1, we might apply relevant meta-analysis techniques to synchronise them into one meta-model, in the presence of the updating data identified in Phase 1 – the IPD not used to develop the historic prognostic model(s). Stacked regressions will be used for this purpose.[27] Stacked regressions simultaneously update, discover and estimate the best combination of literature models in the updating data. They treat the predictions from each model as a predictor variable of the meta-model and subsequently create a linear combination of model prognostics. In particular, stacked regressions directly combine all original literature models into a meta-model by estimating unknown parameters from the updating data.

This approach offers a unique opportunity to update and combine any existing models using large datasets across a wide range of populations and settings [55-57]. This will enhance the potential generalisability of the resulting prognostic model across subgroups, settings and countries [58]. Aggregation techniques will be most appropriate if the validation samples are relatively small. If

Aggregation techniques will be most appropriate if the validation samples are relatively small. If large amounts of data are available and patient populations from literature models are too heterogeneous with the validation population, developing a novel model may be the best strategy, using the available IPD from Phase 1[27]. Extensive updating strategies use more information from the updating dataset than the original dataset and may therefore lead to overfitting. Consequently, if extensive strategies are required, shrinkage will be applied towards the original prognostic model according to the relative sizes of the original and updated datasets to adjust for potential overfitting [59].

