Improving prediction of psychosis in ARMS using a clinically useful prognostic tool (IPPACT)

Protocol

1. Background and Rationale

Psychotic disorders such as schizophrenia have a lifetime prevalence of over 1% and are among the world's leading causes of disability [1]. They have a major detrimental effect on individuals' personal, social and educational functioning [2], and a high economic impact, costing the UK economy £11.8bn per year in direct healthcare costs, lost productivity and costs to carers [3].

It is now possible to identify individuals at high and imminent risk of developing a first episode of psychosis through specific criteria known as "At Risk Mental State" (ARMS) or "Ultra High Risk" (UHR) criteria [4, 5]. People meeting the ARMS criteria have low grade "psychotic –like symptoms" that cause distress. About 15 - 22% of ARMS individuals develop a full psychotic disorder such as schizophrenia within 12 months [5, 6]. Identification of ARMS individuals therefore presents the opportunity for early intervention to prevent of onset of full psychotic disorder.

It is estimated that over 12,000 people in England per year present to clinical services with distressing psychotic-like ARMS symptoms [7]. In recognition of the scale of the problem and the potential benefits of early detection and intervention in the ARMS group, assessment and management of ARMS individuals is included in NICE guidelines for children, young people and adults [8, 9], and since April 2016 NHS England has required clinical services to treat people with the ARMS [10, 11]. A specialised instrument, the Comprehensive Assessment of At Risk Mental States (CAARMS) [12], developed by Principal Investigator [name], is freely available to all clinical services in the UK to detect and monitor the ARMS.

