Finally, **Phase 3** will be a cohort study of ARMS individuals with 12 month follow up to assess the external validity of the new prognostic tool. In addition, a valid prognostic tool could lead to more cost-effective pathways and management plans. To this end the project also includes health economic modelling.

2. Why this Research is Needed Now

Since April 2016 NHS England has required all Early Intervention in Psychosis Services to assess and manage individuals with an ARMS. This has resulted in a huge expansion in number of assessments and individuals accessing care at these services. While NHS England allocated additional funding for services, the extra demand has far exceeded that which was expected, resulting in larger caseloads and a strain on resources. Research to better stratify ARMS patients according to levels of risk of psychosis could reduce this strain, through more efficient use of NHS resources. Thus, those at highest risk could be offered CBT, while lower risk patients could be offered less costly and less intensive regular mental state monitoring. In this way, a prognostic tool that can be used in routine practice in Early Intervention Services will lead to the development of more cost-effective pathways and management plans.

While much ARMS research has attempted to identify the predictors of development of psychosis, including the development of prognostic models, no prognostic tool has yet been implemented in the NHS. Two recent systematic reviews summarised these ARMS studies [14, 15]. Both reviews found that only 7 studies of prognostic models in the ARMS group had any validation procedure. All 7 of these used internal validation only; that is, used the same sample that the model was derived from to test its predictive ability. None had any external validation. Furthermore, all 7 studies used pre-defined prognostic factors and so may have missed assessing other factors likely to be predictive of psychosis. Other problems included small sample sizes, poor reporting of missing data and low number of individuals developing psychosis relative to the number of predictor variables (i.e. low event to predictor variable (EPV) ratio, which might increase the risk of overfitting and overestimating the performance of the model [16, 17]). The development and external validation of one prognostic model has been published [18, 19] (not included in the above reviews).

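### Size-weighted shrinkage towards the original model, with no recalibration of that target and no exemption for the intercept, partly undoes the intercept update and can miscalibrate the updated tool

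*Protocol*

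**What the plan says.** Protocol section 4.2.1 ties the choice of updating method to how far the updating data differ from the data used to develop the model. Small differences call for simple coefficient updating, but "if larger changes are observed more involved methods such as a meta-model approach may be required".

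Section 4.2.1.1 sets out a hierarchy of updating methods. The simplest changes the intercept so that the "mean predicted probability of the event according to the prognostic model becomes equal to the observed event rate in the updating data". Logistic calibration (intercept and overall slope) is the next step, and model revision goes further.

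Section 4.2.1.2 then warns: "Extensive updating strategies use more information from the updating dataset than the original dataset and may therefore lead to overfitting". Its remedy is that "shrinkage will be applied towards the original prognostic model according to the relative sizes of the original and updated datasets". The stated purpose is to adjust for overfitting. Just before this, the section gives another route: with large amounts of data, and where "patient populations from literature models are too heterogeneous with the validation population, developing a novel model may be the best strategy".

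Section 4.2.1.3 assesses the updated model by a calibration plot and the c-index. Section 4.3.6 treats calibration-in-the-large and calibration slope as sufficient for the external validation in Phase 3.

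**The concern.** The sentence fixes a target (the original model) and a weight (relative dataset size). It says nothing of recalibrating the target or of treating the intercept separately. Section 4.2.1.1 classes intercept update and logistic calibration as updating methods, so in the protocol's own terms a recalibrated model is already an updated model. An analyst who follows the text would therefore shrink towards the equation as published, intercept included.

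The intercept is not where overfitting lies. It carries the baseline risk, which the updating data estimate directly. Mixing in the original intercept brings back part of a real difference between populations. The protocol's own figures show that such differences are possible. Section 1 states: "About 15 - 22% of ARMS individuals develop a full psychotic disorder such as schizophrenia within 12 months". Section 4.3.6 gives 35-41% in early studies, over 25% in recent local services, and 20% for planning. A tool whose mean prediction has been shifted in this way would enter Phase 3 with a calibration error introduced by the plan.

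**Working it through.** **Inputs from the protocol.** 12-month transition rates: 15-22% (section 1); 35-41% in early studies, over 25% locally, 20% planned (section 4.3.6). The protocol gives no shrinkage factor, dataset size or coefficient, so there is no stated figure to reproduce.

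**Assumptions.** The ratio of original to updating dataset size runs from 0.1 to 2. Read literally, each coefficient, including the intercept, becomes

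shrunk = w × original + (1 − w) × re-estimated, with w = n_original / (n_original + n_updating).

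**Step 1: intercept-only check by hand.** Take an original rate of 35% and an updating rate of 20%. On the log-odds scale, ln(0.35/0.65) = −0.619 and ln(0.20/0.80) = −1.386.

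- Equal sizes, w = 0.5: 0.5 × (−0.619) + 0.5 × (−1.386) = −1.003, a risk of 26.8%. E/O = 26.8/20 = 1.34.
- Original twice as large, w = 0.667: −0.875, a risk of 29.4%. E/O = 1.47.
- Original one tenth as large, w = 0.091: −1.317, a risk of 21.1%. E/O = 1.06.

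**Step 2: with a predictor.** One standard-normal predictor is assumed, with a log-odds slope of 1.0 in the original data and 0.6 in the updating data. E/O in the updating population, with everything shrunk:

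| Original vs updating rate | Ratio 0.1 | 0.5 | 1 | 2 |
|---|---|---|---|---|
| 41% vs 20% | 1.08 | 1.32 | 1.50 | 1.68 |
| 35% vs 20% | 1.06 | 1.23 | 1.36 | 1.49 |
| 15% vs 25% | 0.95 | 0.84 | 0.77 | 0.71 |
| 22% vs 20% | 1.01 | 1.03 | 1.05 | 1.06 |
| 20% vs 20% | 1.00 | 1.00 | 0.99 | 1.00 |

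The pull grows with the difference in rates and with the original dataset's share. It is always partial.

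**Step 3: with sampling error.** Simulation for 35% vs 20%, with assumed sizes, gave E/O of about 1.31 at 300 original and 300 updating participants. At 600 and 300 it gave 1.43 to 1.45 in two separate runs.

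**Step 4: the two repairs.** In the Step 2 setting, shrinking towards the original model after an intercept update gives E/O of 0.99 to 1.00. Shrinking the slopes and re-estimating the intercept gives 1.00.

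**Step 5: is the weight itself at fault?** Simulation with six original predictors and one new factor, 35% vs 20%, 300 participants in each dataset (lower log loss is better):

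| Method | Log loss |
|---|---|
| Everything shrunk to the original model | 0.4745 |
| No shrinkage | 0.4686 |
| Recalibrate first, then shrink | 0.4659 |
| Coefficients only, by dataset size | 0.4638 |

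The harm comes through the intercept. Size-weighted shrinkage of the coefficients alone did no harm here and had the lowest log loss of the four.

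**The case against.** The strongest reply is that the protocol never says the original model is left un-recalibrated, nor that the intercept is shrunk. The sentence carries a citation on updating and shrinkage, whose content cannot be checked here, and details of this kind often go to the analysis plan. This stands in part: the text is silent, and an analyst might well exempt the intercept. But the protocol does fix the target and the weight, and following those words can give a worse model than no shrinkage. That is more than a missing detail.

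The safeguards are also cited. The route to a novel model counts, but it needs large data and too much heterogeneity together, and it is only described as possibly best. Section 4.2.2 adds a novel model if updating performs poorly, with discrimination as its main worry; an intercept shift leaves the c-index unchanged. The plot of section 4.2.1.3 would show a gross shift, but no correction is tied to it.

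Three stronger readings are tempting and are not supported:

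- A reader might infer that the rule restores the original baseline risk. It moves the prediction only part of the way, and only slightly when the updating data dominate.
- A reader might infer that it does so exactly when populations differ most. Section 4.2.1.2 defines extensive updating by the information taken from the updating data, and it offers another route for very different populations when data are large.
- A reader might infer that size-based weighting is itself wrong, because section 2 describes earlier models as having a "low number of individuals developing psychosis relative to the number of predictor variables" and so a risk of overfitting. That describes the general literature, whereas section 4.2.1 limits updating to models judged statistically valid. Step 5 gives no support for replacing the weight.

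**Conclusion.** The concern holds in a limited form. The shrinkage sentence, followed as written, partly undoes the intercept update and shifts mean predicted risk towards the original population's rate. Under the assumed sizes and coefficients, predicted events exceed observed events by about 30% to 45% for 35% vs 20% at size ratios of 1 to 2. The error runs the other way when the original rate is the lower one (E/O 0.77 to 0.71 for 15% vs 25% at the same ratios). For 22% vs 20%, E/O is at most 1.06. When the original dataset is one tenth of the updating data, E/O stays between 0.95 and 1.08 for the pairs tabulated. The size in practice therefore depends on which model is updated and how much new participant data is obtained, neither of which the protocol can know yet. The sentence should be amended before the updating analysis, because the affected property is one that Phase 3 is designed to test.

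**What to change.** Amend the shrinkage sentence in section 4.2.1.2 to state three things in order:

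1. The original model is first recalibrated to the updating data (intercept, or intercept and overall slope).
2. Shrinkage applies to predictor effects only, towards that recalibrated model. The weight by relative dataset size may stay; a shrinkage factor estimated from the updating data is an optional alternative.
3. The intercept is re-estimated last in the updating data and is never shrunk.

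The cost is one sentence and a few lines of code. No new data are needed and the sample size does not change.
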